7.2 Medical History

Medical history data will be summarized and presented using body systems and conditions/diagnoses as captured on the eCRF. The body systems will be presented in alphabetical order and the conditions/diagnoses will be presented in alphabetical order within each body system. The number and percentage of subjects with a particular condition/diagnosis will be summarized for each treatment arm. Subjects reporting more

than one condition/diagnosis within a body system will be counted only once for that body system.

7.3 Prior, Concomitant and Post-Treatment Medications

A prior medication is defined as any medication taken prior to the date of the first dose of study drug (ABT-493/ABT-530 or SOF + RBV). A concomitant medication is defined as any medication that started prior to the date of the first dose of study drug and continued to be taken on or after the first dose of study drug or any medication that started on or after the date of the first dose of study drug, but not after the date of the last dose of study drug. A post-treatment medication for the treatment of HCV is defined as any medication taken on or after the last dose of study drug and entered as "Post-treatment HCV medications" on the eCRF.

The number and percentage of subjects taking prior medications, concomitant medications, and post-treatment HCV medications will be summarized for each treatment arm by generic drug name based on the WHO Drug Dictionary. Prior medications will be divided by the following categories:

- The prior anti-HCV medications taken by treatment experienced subjects;
- All other prior medications for all treated subjects.

8.0 Patient Disposition

The number and percentage of subjects who screen failed for any reason, and for each screen failure reason, will be summarized for all subjects who screen failed.

8.1 Disposition of Safety Population

The number of subjects in each of the following categories will be summarized by investigator for each treatment arm and overall.

- Randomized subjects;
- Subjects who took at least one dose of study drug;

- Subjects who completed study drug;
- Subjects who prematurely discontinued study drug;
- Subjects who completed the study;
- Subjects who prematurely discontinued from the study;
- Subjects ongoing in the Post-Treatment Period at the time of the primary analysis.

The number and percentage of subjects who discontinued study drug will be summarized by reason (all reasons) and by primary reason (per eCRF) for each treatment arm and overall. Similar summaries will be provided for discontinuations from the study.

The number and percentage of subjects with reported study drug interruptions will be summarized by treatment arm.

Reasons for study drug interruptions will be presented in the CSR listings.

9.0 Study Drug Exposure and Compliance

9.1 Exposure

The duration of exposure to study drug will be summarized for the safety population. Duration of exposure is defined for each subject as the last study drug dose date minus the first study drug dose date plus 1 day.

The safety population will be used to summarize the duration of exposure for each treatment arm and for the study total.

Descriptive statistics (mean, standard deviation, median, minimum, and maximum) will be presented for exposure during the treatment period.

Study drug duration will be summarized with frequencies and percentages using the following categories:

- 1 to 15 days

- 16 to 30 days
- 31 to 45 days
- 46 to 60 days
- 61 to 75 days
- 76 to 90 days
- > 90 days

In addition, the number and percentage of subjects with a study drug duration of ≥ 52 days for Arm A and ≥ 77 days for Arm B will be summarized.

9.2 Compliance

At each visit (starting with the Week 4 visit) during the Treatment Period, the total number of tablets dispensed and returned is recorded. The compliance for study drug (ABT-493/ABT-530, SOF, and RBV) during the treatment period will be calculated as the percentage of tablets taken relative to the total tablets expected to be taken. The total number of tablets expected to be taken will be equal to the total number of tablets that should have been taken per the protocol for the duration that the subject was in the Treatment Period (date of last dose of study drug – date of first dose of study drug + 1). Study drug interruptions recorded on the eCRF will not be subtracted from the duration. For compliance to RBV, RBV dose modifications due to adverse events, toxicity management, or weight changes as recorded on the RBV Dose Modifications eCRF will be used to modify the total number of tablets that should have been taken.

A subject is considered to be compliant to each study drug if the percentage of compliance for that type is between 80% and 120%. Compliance will be calculated for each subject and each tablet type by treatment arm and summarized with the mean, median, standard deviation, minimum, and maximum. The percentage of compliant subjects will be summarized for each study drug and each treatment arm, based on data as observed. An additional summary of the percentage of compliant subjects will be provided where subjects who are missing study drug accountability records will be imputed as non-compliant.

10.0 Efficacy Analysis

10.1 General Considerations

General Considerations

Treatment effects will be evaluated based on a 2-sided significance level of 0.050 (when rounded to three decimal places), and all efficacy analyses will be performed on the ITT population, unless otherwise specified.

Missing data will be imputed as described in Section 6.3 for analyses of the HCV RNA endpoints of SVR.

Plasma HCV RNA levels will be determined for each sample collected by the central laboratory using the Roche COBAS[®] AmpliPrep/COBAS[®] TaqMan[®] HCV Quantitative Test, v2.0. The lower limit of detection (LLOD) and lower limit of quantification (LLOQ) for this assay (regardless of genotype) are both 15 IU/mL.

HCV RNA results that are detectable but not quantifiable are reported as "< 15 IU/ML HCV RNA DETECTED" and those that are undetectable are reported as "HCV RNA NOT DETECTED" in the database.

The notation "HCV RNA < LLOQ" is used to represent all HCV RNA values < 15 IU/mL, including values reported as "HCV RNA NOT DETECTED" or "< 15 IU/ML HCV RNA DETECTED." HCV RNA \geq LLOQ are all quantifiable values.

IL28B rs12979860 will be resulted as C/C, C/T, or T/T by the central laboratory.

Definitions for Efficacy Endpoints

A confirmed quantifiable value during treatment is defined as any two consecutive HCV RNA measurements \geq LLOQ (or 100 IU/mL for **Breakthrough**), either both during treatment or at the final treatment measurement and the next consecutive post-treatment measurement. A confirmed quantifiable post-treatment value is defined as any two consecutive post-treatment HCV RNA measurements \geq LLOQ.

Breakthrough = confirmed HCV RNA \geq 100 IU/mL after HCV RNA $<$ LLOQ during the Treatment Period; or confirmed increase from nadir in HCV RNA (two consecutive HCV RNA measurements $>$ 1 \log_{10} IU/mL above nadir) at any time point during the Treatment Period. A single breakthrough value (\geq 100 IU/mL or $>$ 1 \log_{10} above nadir) followed by lost to follow-up also will be considered a breakthrough (i.e., will not require confirmation).

EOT failure = HCV RNA \geq LLOQ at end of treatment with at least 6 weeks of treatment, where the HCV RNA value must be collected on or after Study Drug Day 36 and study drug duration \geq 36 days.

On-treatment virologic failure = Breakthrough or EOT failure.

SVR₄ = HCV RNA $<$ LLOQ in the SVR₄ window (4 weeks after the last actual dose of study drug) without any confirmed quantifiable (\geq LLOQ) post-treatment value before or during that SVR window.

SVR₁₂ = HCV RNA $<$ LLOQ in the SVR₁₂ window (12 weeks after the last actual dose of study drug) without any confirmed quantifiable (\geq LLOQ) post-treatment value before or during that SVR window.

SVR₂₄ = HCV RNA $<$ LLOQ in the SVR₂₄ window (24 weeks after the last actual dose of study drug) without any confirmed quantifiable (\geq LLOQ) post-treatment value before or during that SVR window.

Relapse₄ = confirmed HCV RNA \geq LLOQ between end of treatment and 4 weeks after last actual dose of study drug (up to and including the SVR₄ assessment time point) for a subject with HCV RNA $<$ LLOQ at Final Treatment Visit who completed treatment (defined as study drug duration \geq 52 days for Arm A and \geq 77 days for Arm B), excluding reinfection as described below.

Relapse₁₂ = confirmed HCV RNA \geq LLOQ between end of treatment and 12 weeks after last actual dose of study drug (up to and including the SVR₁₂ assessment time point) for a

subject with HCV RNA < LLOQ at Final Treatment Visit who completed treatment (defined as study drug duration ≥ 52 days for Arm A and ≥ 77 days for Arm B), excluding reinfection as described below.

Relapse₂₄ = confirmed HCV RNA \geq LLOQ within the SVR₂₄ window for a subject who achieved SVR₁₂ and has HCV RNA data available in the SVR₂₄ window, excluding reinfection.

Relapse_{overall} = confirmed HCV RNA \geq LLOQ between end of treatment and up to and including the last HCV RNA measurement collected in the PT Period for a subject with HCV RNA < LLOQ at Final Treatment Visit who completed treatment (defined as study drug duration ≥ 52 days for Arm A and ≥ 77 days for Arm B), excluding reinfection.

Only subjects who have at least one post-treatment HCV RNA value will be included in analyses of relapse. For the analysis of relapse, completion of treatment is defined as any subject with study drug duration of 52 days or greater for Arm A and 77 days or greater for Arm B. If the last available post-treatment value is \geq LLOQ, then the subject will be considered a relapse (i.e., will not require confirmation).

HCV reinfection is defined as confirmed HCV RNA \geq LLOQ after the end of treatment in a subject who had HCV RNA < LLOQ at Final Treatment Visit, along with the post-treatment detection of a different HCV genotype, subtype, or clade compared with baseline, as determined by phylogenetic analysis of the NS3 or NS5A, and/or NS5B gene sequences. Reinfection in the case of the same HCV subtype is defined as a clade switch, as indicated by the lack of clustering between the baseline and post-treatment sequences by phylogenetic analysis. If phylogenetic analysis is not possible due to technical difficulties, HCV reinfection may be determined with a confirmed HCV genotype or subgenotype switch by the Versant HCV Genotype Inno-LiPA Assay v2.0 or Sanger assay.

Post-treatment relapse is defined as described earlier (**Relapse₁₂**, **Relapse₂₄**, **Relapse_{overall}**), and no genotype, subtype, or clade switch compared with baseline as

determined by phylogenetic analysis of the NS3 or NS5A gene sequences. If phylogenetic analysis is not possible due to technical difficulties, the subject will be defined as having a post-treatment relapse unless an HCV genotype or subgenotype switch is confirmed by the Versant HCV Genotype Inno-LiPA Assay v2.0 or Sanger assay.

Reasons for SVR₄ Non-Response

Subjects who do not achieve SVR₄ (SVR₄ non-responders) will be categorized as having:

1. On-treatment virologic failure (see **On-treatment virologic failure** definition);
2. Relapse by Post-Treatment Week 4 (defined according to the **Relapse₄** definition for subjects who complete treatment);
3. Prematurely discontinued study drug with no on-treatment virologic failure (defined as any SVR₁₂ non-responder who prematurely discontinued study drug [study drug duration < 52 days for subjects in Arm A, and < 77 days for subjects in Arm B] and did not meet the **On-treatment virologic** failure definition);
4. HCV reinfection (see definition described earlier);
5. Missing follow-up data in the SVR₄ window (defined as any subject who completed study drug without data in the SVR₄ window after applying the imputation rules and not meeting the definitions of [1], [2], [3], or [4]);
6. Other (defined as any SVR₄ non-responder not meeting the definitions of [1] – [5]).

Reasons for SVR₁₂ Non-Response

Subjects who do not achieve SVR₁₂ (SVR₁₂ non-responders) will be categorized as having:

1. On-treatment virologic failure (see **On-treatment virologic failure** definition);

2. Relapse (defined according to the **Relapse₁₂** definition for subjects who complete treatment);
3. Prematurely discontinued study drug with no on-treatment virologic failure (defined as any SVR₁₂ non-responder who prematurely discontinued study drug [study drug duration < 52 days for subjects in Arm A, and < 77 days for subjects in Arm B] and did not meet the **On-treatment virologic failure** definition);
4. HCV reinfection (see definition described earlier);
5. Missing follow-up data in the SVR₁₂ window (defined as any subject who completed study drug without data in the SVR₁₂ window after applying the imputation rules and not meeting the definitions of [1], [2], [3], or [4]);
6. Other (defined as any SVR₁₂ non-responder not meeting the definitions of [1] – [5]).

Reasons for SVR₂₄ Non-Response

Subjects who do not achieve SVR₂₄ (SVR₂₄ non-responders) will be categorized as having:

1. On-treatment virologic failure (see **On-treatment virologic failure definition**);
2. Relapse (defined according to the **Relapse₁₂** definition for subjects who complete treatment);
3. Relapsed after achieving SVR₁₂ (see **Relapse₂₄** definition);
4. Prematurely discontinued study drug with no on-treatment virologic failure (defined as any SVR₂₄ non-responder who prematurely discontinued study drug [study drug duration < 52 days for subjects in Arm A, and < 77 days for subjects in Arm B] and did not meet the **On-treatment virologic failure, Relapse₁₂, or Relapse₂₄** definitions);
5. HCV reinfection;

6. Missing follow-up data in the SVR₂₄ window (defined as any subject who completed study drug without data in the SVR₂₄ window after applying the imputation rules and not meeting the definitions of [1], [2], [3], [4], or [5]);
7. Other (defined as any SVR₂₄ non-responder not meeting the definitions of [1] – [6]).

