6.3 Missing Data Imputation

Missing Data Imputation for SVR

HCV RNA values will be selected for analysis based on the analysis windows defined in Section 6.2. HCV RNA values from central laboratory will be used as described in Section 10.1, unless otherwise specified.

For analyses of SVR, subjects missing a visit HCV RNA value will have backward imputation applied, if possible. For backward imputation, if the nearest HCV RNA value after the SVR window is unquantifiable or undetectable, then it will be used to impute the HCV RNA value in the SVR window. If a subject continues to be missing an HCV RNA value within the appropriate SVR window after performing backward imputation, then this value will be imputed using an HCV RNA value from a local laboratory if available; otherwise, the HCV RNA value for that window will be considered missing. Subjects with missing HCV RNA data in the analysis window, after applying these imputations, will be imputed as a failure of viral response.

Regardless of the imputation method described above, if a subject starts another treatment for HCV, then all HCV RNA values for this subject measured on or after the start date of the new HCV treatment will be excluded from analyses. The subject will be considered a failure for summaries of viral response at all time points after the start of the new HCV treatment.

Missing Data Imputation for Virologic Failure

If HCV RNA values from the central laboratory are missing but a local laboratory value is available in the appropriate time period, then the local laboratory data will be used to assess post-treatment relapse and on-treatment virologic failure.

Missing Data Imputation for PRO Questionnaires

For EQ-5D-3L index and VAS scores, no imputation will be performed for missing items. The missing items of the FSS questionnaire will be imputed with the average score of the answered items as long as more than 50% of the items on the FSS are answered.

If a subject starts another treatment for HCV, then all PRO values for this subject measured on or after the start date of the new HCV treatment will be excluded from analyses.

No imputation will be performed for missing data in other than specified above.

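### Relapse₂₄ requires SVR₁₂, so a completer with no SVR₁₂-window value who is viremic at Week 24 is classed as missing, then as other, and not as a relapse

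*SAP*

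**What the plan says.** All references are to the SAP.

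- **Windows (Section 6.2, Table 3).** SVR₁₂ uses Study Drug End Days 57–126 and SVR₂₄ uses Days 127–210. The last value in the window counts.
- **Missing SVR values (Section 6.3).** A later value fills a gap only "if the nearest HCV RNA value after the SVR window is unquantifiable or undetectable". A local laboratory value is tried next. A subject still without a value is a failure.
- **Relapse₁₂ (Section 10.1).** It covers completers who were < LLOQ at the Final Treatment Visit, from end of treatment to the SVR₁₂ assessment.
- **Relapse₂₄ (Section 10.1).** It is a confirmed quantifiable value in the SVR₂₄ window "for a subject who achieved SVR₁₂ and has HCV RNA data available in the SVR₂₄ window".
- **Relapse_overall (Section 10.1).** It has the same entry conditions as Relapse₁₂ but runs "up to and including the last HCV RNA measurement collected in the PT Period". Section 10.8 tabulates it by SVR window.
- **Last-value rule (Section 10.1).** If the last available post-treatment value is ≥ LLOQ, "then the subject will be considered a relapse (i.e., will not require confirmation". No endpoint is named.
- **Reasons for non-response (Section 10.1).** SVR₁₂ reason 5, missing follow-up data, is "any subject who completed study drug without data in the SVR₁₂ window after applying the imputation rules" who fits no higher reason. SVR₂₄ reason 3 is "Relapsed after achieving SVR₁₂", with a pointer to Relapse₂₄. SVR₂₄ reason 7 is the residual class.
- **Section 10.6.1.** One sensitivity analysis counts SVR₁₂ non-responders as successes if their reason is early discontinuation without on-treatment failure, or missing follow-up data.

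**The concern.** Relapse₁₂ ends at the SVR₁₂ assessment, and Relapse₂₄ starts only for subjects who achieved SVR₁₂. A completer whose SVR₁₂ value is missing falls between the two. If that subject is viremic at Week 24, the relapse has been observed, yet neither reason table shows it as virologic failure. The SVR₂₄ table puts it in the residual class.

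Week 24 data also work in one direction only. An unquantifiable Week 24 value turns a missing SVR₁₂ into a success. A quantifiable one leaves it missing, and Section 10.6.1 then makes that a success as well. In that sensitivity analysis a completer with no SVR₁₂-window value is a success whichever way the Week 24 result falls.

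At stake are the SVR₂₄ reason table, the Relapse₂₄ count and one sensitivity analysis of the primary endpoint. The primary analysis is not at stake.

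**Working it through.** The plan states no figure on this point that could be reproduced. The check is to run the stated rules on test subjects. All of them completed treatment, were < LLOQ at the Final Treatment Visit, were not reinfected, started no new HCV treatment and have no local laboratory values. The last-value rule is read as waiving confirmation within each endpoint's own time limit.

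**The central case.** Values are < LLOQ up to Day 56, there is none on Days 57–126, and Day 168 is ≥ LLOQ and is the last value.

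1. SVR₁₂: the window is empty. The next value is quantifiable, so backward imputation is not allowed. The subject is a failure.
2. Relapse₁₂: there is no quantifiable value by Day 126, so it is not met.
3. Relapse₂₄: SVR₁₂ was not achieved, so it is not met.
4. SVR₁₂ reason: reasons 1–4 do not apply and the window is empty, so reason 5 (missing).
5. SVR₂₄ reason: reasons 1–5 do not apply. Reason 6 (missing) does not apply because Day 168 lies in the window. Reason 7 (other) remains.
6. Relapse_overall: met.

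**Variations, to find the limits of the gap.**

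| Post-treatment values | SVR₁₂ result or reason | SVR₂₄ result or reason | Relapse₁₂ | Relapse₂₄ | Relapse_overall |
|---|---|---|---|---|---|
| Negative to Day 56, none on Days 57–126, positive Day 168 | Missing | Other | No | No | Yes |
| Same, but Week 8 sample drawn on Day 58 | SVR₁₂ achieved | Relapse₂₄ | No | Yes | Yes |
| Same as first row, but late sample on Day 215 | Missing | Missing | No | No | Yes |
| Misses Week 12, negative at Week 24 | SVR₁₂ achieved (imputed) | SVR₂₄ achieved | No | No | No |
| Only a Week 2 value, negative | Missing | Missing | No | No | No |
| Only a Week 2 value, positive | Relapse₁₂ | Relapse₁₂ | Yes | No | Yes |

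The gap needs an SVR₁₂ window with no value at all. A missed Week 12 visit is not enough, because a Week 8 sample on Day 57 or later closes it. The residual class at SVR₂₄ also needs the late sample to fall on Days 127–210.

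**Effect of the label in Section 10.6.1.** The first-row subject carries the missing label and is therefore set to success. At the planned arm sizes this moves the SVR₁₂ rate in that analysis by 1/80 = 1.25 points in Arm A or 1/40 = 2.5 points in Arm B. This presumes that the late value is in the database used for the analysis. Section 4.4 places the primary analysis at Week 12 and the final analysis at Week 24.

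**Primary endpoint.** The subject is an ITT failure with or without the gap, so the non-inferiority result is unchanged.

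**How often.** The plan gives no rate. As an assumption, let 3% to 10% of the 120 subjects have no SVR₁₂-window value and 2% to 5% of those relapse. The expected number is 120 × 0.03 × 0.02 = 0.07 to 120 × 0.10 × 0.05 = 0.6 subjects, before requiring a return visit on Days 127–210.

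**The case against.** The strongest reply is that the relapse is not lost. Relapse_overall counts it, and Section 10.8 reports it by window with subject numbers. Section 10.1 names Relapse_overall within post-treatment relapse, so Section 10.9 can bring the subject into the primary virologic failure population, and the final report updates the resistance listings for failures after Week 12. This stands. A reader might infer that the rules have no place at all for this subject, and the plan does not support that. What remains is a conflict: the same subject is a relapse in one table and other in the next.

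A second reply is that missing is an accurate label at Week 12. Viremia first seen at Week 24 after earlier negative values cannot be dated to before Week 12, and the secondary endpoint in Section 10.5 is relapse within 12 weeks. This also stands. It is tempting to move such a subject into Relapse₁₂, but the definition does not allow it. The subject's exclusion from the mITT-GT-VF population follows from the same label and is accepted here for the same reason.

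A third inference concerns the relapse denominator: "Only subjects who have at least one post-treatment HCV RNA value will be included in analyses of relapse". One might read this as counting any completer with a single sample as relapse-free. It does not, because a last value ≥ LLOQ counts as a relapse. Only completers whose available values show no relapse are counted that way. Requiring Week 12 data of them would keep early relapsers while dropping negative subjects who left, so inclusion would depend on outcome. The effect is also slight: if 4 of 78 completers lacked Week 12 data (an assumption), 2/78 = 2.6% would become 2/74 = 2.7%.

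Finally, the last-value rule could be read broadly enough to make the subject a relapse for every endpoint. Its parenthesis speaks only of confirmation, and the broad reading would override the Relapse₁₂ time limit. Two programmers could still differ, so the sentence needs a limit.

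**Conclusion.** The point holds as a definitional gap. Followed as written, the SAP files an observed late relapse under other in the SVR₂₄ reasons, leaves it out of Relapse₂₄, and lets one sensitivity analysis count a subject with later viremia as an SVR₁₂ success.

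The conclusion rests on the narrow reading of the last-value rule and on a completer with no SVR₁₂-window value and a quantifiable value on Days 127–210, without reinfection or new HCV treatment. Such subjects will be few, probably fewer than one under the ranges assumed above. Each is worth 1.25 points in Arm A or 2.5 points in Arm B. The primary ITT comparison and the Week 12 relapse endpoint do not change. The case for acting is that the tables would contradict each other and that the correction is very cheap.

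**What to change.** 1. **Relapse₂₄ and SVR₂₄ reason 3 (Section 10.1).** Extend both to completers who were < LLOQ at the Final Treatment Visit, did not meet Relapse₁₂ and have a missing SVR₁₂ value after the Section 6.3 rules. A confirmed or last-available HCV RNA ≥ LLOQ in the SVR₂₄ window, before any new HCV treatment and without reinfection, is then a relapse and not other. Reword reason 3 so that it no longer presupposes SVR₁₂.
2. **Section 10.6.1.** Do not impute success for an SVR₁₂ non-responder in the missing class who has a later observed HCV RNA ≥ LLOQ.
3. **Last-value rule (Section 10.1).** State that it waives confirmation within each relapse endpoint's own time limit.

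Leave the Relapse₁₂ definition, its denominator and the SVR₁₂ reason as they are.

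The cost is a few lines of wording and code. The count of late relapses can only stay the same or rise, and the SVR₁₂ rate in the affected sensitivity analysis can only stay the same or fall.
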